8.3 Maintenance Procedures

NOTE: Subjects with unknown HBV status not previously tested in screening and receiving carfilzomib should be tested for HBV as indicated in Section 7.

8.3.1 Throughout the Maintenance Period

- **AEs:** Record all AEs per the NCI CTCAEv4.03.
- **Concomitant Medications:** Record any changes in concomitant medications. Concomitant medications include but are not limited to over the counter medications, supplements, and vitamins.
- **Disease Evaluation:**
 - Skeletal Survey (if clinically indicated)
 - Assess extramedullary plasmacytomas (if clinically indicated): PET/CT and/or WB-MRI

8.3.2 Day 1 Cycles 1+ (unless otherwise noted)

- **Physical Exam:** Symptom-directed physical exam (to include weight). Subjects should also be monitored for second primary malignancies. If a subject's weight changes by more than 10% from induction C1D1, the dose of elotuzumab should be re-calculated. This re-calculated weight should be used as the new baseline weight. For office visits required during the COVID-19 pandemic, virtual visits will be allowed per investigator discretion.
- **Performance Status:** ECOG performance status. For required time-points during the COVID-19 pandemic, performance status may be performed virtually if the office visit is being performed virtually
- **Vital Signs:** Vital signs should include temperature, heart rate, blood pressure and respiratory rate. Measure prior to elotuzumab infusion.

- **Laboratory Assessments**

- Serum chemistries: BUN, creatinine, (with calculated creatinine clearance on Day 1 of each cycle), glucose, uric acid, calcium, chloride, phosphorus, potassium, sodium, LDH, albumin, total protein, magnesium, total bilirubin, alkaline phosphatase, AST and ALT. **NOTE:** calcium should also be corrected for albumin.
- CBCD: complete blood count with differential and platelets
- Pregnancy test (serum or urine) in FCBP.

- **Disease Evaluation:**

- Blood and urine tests: Serum QIg (including IgA, IgM, IgG, IgD, IgE), SPEP, UPEP (24-hr urine sample required), serum and urine immunofixation, and serum FLC. Testing for IgD and IgE will only be performed for subjects with IgD and IgE-type myeloma. Serum FLC to be performed for subjects with light chain only disease and for subjects where a CR is suspected or maintained. Subjects without measurable urine M-Protein at baseline will not be required to have UPEP or urine immunofixation repeated at subsequent disease assessment time-points, unless clinically indicated.
- Bone marrow aspirate and biopsy (see Section 8.8.3): Collected post-induction (within 7 days prior to treatment on C1D1 of maintenance)

8.3.3 Every 6 months for Cycles 1-n

- **Disease Evaluation:**

- Bone marrow aspirate and biopsy (see Sections 7 and 8.8.3): Disease evaluation per standard of care

8.4 Time of CR

- **Disease Evaluation:**

- Bone marrow aspirate and biopsy (see Section 8.8.3)
- Assess extramedullary plasmacytomas: PET/CT and/or WB-MRI

8.5 Time of Disease Relapse/Progression

- **Disease Evaluation:**

- Bone marrow aspirate and biopsy (see Section 8.8.3): At discretion of investigator

8.6 Safety Follow-up Visit

This visit should occur in subjects 30 days (+/-10 days) after treatment stops for whatever reason (toxicity, progression, or at discretion of the investigator). **NOTE:** this 30-day time period applies even if the subject is taken off study treatment and begins new anti-cancer treatment during this time period.

- **Physical Exam:** Symptom-directed physical exam (to include weight). Subjects should also be monitored for second primary malignancies. For office visits required during the COVID-19 pandemic, virtual visits will be allowed per investigator discretion
- **Performance Status:** ECOG performance status. For required time-points during the COVID-19 pandemic, performance status may be performed virtually if the office visit is being performed virtually

- **Vital Signs:** Vital signs should include temperature, heart rate, blood pressure and respiratory rate.
- **Cardiac Evaluation:** ECG
- **Laboratory Assessments**
 - Serum chemistries: BUN, creatinine, glucose, uric acid, calcium, chloride, phosphorus, potassium, sodium, LDH, albumin, total protein, magnesium, total bilirubin, alkaline phosphatase, AST and ALT. **NOTE:** calcium should also be corrected for albumin.
 - CBCD: complete blood count with differential and platelets
- **AEs:** Record all AEs; subjects who have ongoing Grade 4 AE or SAE at the time of discontinuation from treatment, and those who come off treatment prematurely for safety reasons will continue to be followed until the event is resolved or deemed irreversible by the investigator.
- **Concomitant Medications:** Record any changes in concomitant medications. Concomitant medications include but are not limited to over the counter medications, supplements, and vitamins.

8.7 Follow-up

For subjects who discontinue study treatment before relapse or PD, disease evaluations should continue to be performed until relapse or confirmed PD, death, start of a new anticancer treatment, withdrawal of consent to study participation, or until the criteria for the final analysis are met (Section 14.5.1) whichever occurs first. The schedule for disease evaluation should follow the schedule outlined during maintenance. Survival follow-up will occur every 3 months (+/- 30 days) from the last administration of protocol-directed therapy until death, lost to follow-up, or until the criteria for the final analysis are met (Section 14.5.1) and may be conducted via telephone. Any second primary malignancies discovered during long-term follow-up will be documented. Follow-up clinical information may also be obtained through chart reviews or other data sources (e.g. death registries).

The investigator is responsible for following the subject during the required follow-up period even if the subject lives elsewhere or has been released from his or her care and is being treated at another institution.

If the subject cannot be contacted following three attempted telephone calls over a period of 10 business days, the subject will be contacted in writing. Lost to follow-up is defined as four consecutive unsuccessful documented attempts (telephone and written) to contact the subject.

NOTE: in the event the criteria for the final analysis are met, and there are subjects who have not yet been discontinued from study treatment, subjects in follow-up will continue to be followed until all subjects have discontinued study treatment and completed the Safety Follow-up Visit (see above).

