3.2 Inclusion Criteria

Subject must meet all of the following applicable inclusion criteria to participate in this study:

1. Written informed consent and HIPAA authorization for release of personal health information signed by the subject or his/her legally authorized representative.
2. Age \geq 18 years at the time of consent.
3. Eastern Cooperative Oncology Group (ECOG) Performance Status of 0-2 (see Appendix A, Section 18.1).
4. Documented history of relapsed and/or refractory multiple myeloma per IMWG 2016 criteria [22] as defined below (biochemical and/or clinical relapse per IMWG criteria); (**NOTE:** subjects refractory to bortezomib and/or lenalidomide are eligible; subjects who previously received carfilzomib are eligible provided they experienced a minimal response or better and relapsed >60 days after completion of treatment [see exclusion criteria #2]):
 - a. Relapse is defined as progression of disease after an initial response to previous treatment, more than 6 months after discontinuation of treatment.
 - b. Refractory is defined as lack of response to previous treatment, progression of disease during treatment, or progression of disease within 6 months of discontinuation of treatment.
5. Prior treatment with one line (and no more than one line) of systemic therapy for MM; **NOTE:** A new line of therapy is considered to start when a planned course of therapy is modified to include other treatment agents (alone or in combination) as a result of progressive disease (PD), relapse, or toxicity or when a planned period of observation off therapy is interrupted by a need for additional treatment for the disease. Induction therapy and stem cell transplant followed by planned maintenance therapy (provided there is no intervening PD) are considered to be a single line.
6. Subject must have recovered from any treatment-induced toxicities to \leq grade 1 or baseline:
7. Adequate washout from previous therapy:
 - a. Prior chemotherapy is completed >3 weeks prior to day 1 of treatment (6 weeks for melphalan, nitrosoureas or monoclonal antibodies).
 - b. Autologous transplant completed (referring to day of stem cell infusion) >12 weeks prior to day 1 of treatment; allogeneic transplant >16 weeks prior to day 1 of treatment.
 - c. Prior radiotherapy completed at least 2 weeks prior to day 1 of treatment.

- d. Corticosteroid therapy at a dose equivalent to dexamethasone >4mg/day has been completed at least 2 weeks prior to day 1 of treatment.

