³ The post-induction disease evaluation (blood and urine collection and bone marrow biopsy/aspirate) should occur within 7 days prior to treatment on C1D1 of maintenance. The primary endpoint (VGPR or better post induction) will be assessed at this post-induction disease evaluation. See Section 13.1 for details on efficacy evaluations and note that all response categories (CR, sCR, VGPR, PR, and PD) require 2 consecutive assessments.

⁴ A window of +/- 14 days will be applied to all maintenance study visits (includes treatment and required procedures).

⁵ This visit should occur in subjects 30 days (+/-10 days) after treatment stops for whatever reason (toxicity, progression, or at discretion of the investigator). **NOTE:** subjects who have ongoing Grade 4 AE or SAE at the time of the Safety Follow-up Visit will continue to be followed until the event is resolved or deemed irreversible by the investigator.

⁶ For subjects who discontinue study treatment before relapse or PD, disease evaluations should continue to be performed until relapse or confirmed PD, death, start of a new anticancer treatment, withdrawal of consent to study participation, or end of the study, whichever occurs first. The schedule for disease evaluation should follow the schedule outlined during maintenance. Survival follow-up will occur every 3 months (+/- 30 days) from the last administration of protocol-directed therapy or until death, and may be conducted via telephone. Any second primary malignancies discovered during long-term follow-up will be documented.

⁷ Complete physical exam at screening with evaluation by body system, including height, weight and neurologic exam to detect peripheral neuropathy. Thereafter symptom-directed physical exam (to include weight) only. Subjects should also be monitored for second primary malignancies. If a subject's weight changes by more than 10% from induction C1D1, the dose of carfilzomib and elotuzumab should be re-calculated. This re-calculated weight should be used as the new baseline weight.

⁸ Vital signs (to include temperature, heart rate, blood pressure and respiratory rate) should be recorded at screening, before each elotuzumab infusion, and at the Safety Follow-up Visit.

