9. DISCONTINUATION FROM TREATMENT AND STUDY WITHDRAWAL

9.1 Treatment Discontinuation Criteria

Study treatment will continue until one of the following criteria applies:

- Disease relapse or progression
- Intercurrent illness that prevents further administration of treatment
- Unacceptable adverse event(s)
- Subject decides to withdraw study consent
- General or specific changes in the subject's condition render the subject unacceptable for further treatment in the judgment of the investigator
- Study subject becomes pregnant

NOTE: In the event the criteria for the final analysis are met, and there are subjects who have not yet been discontinued from study treatment, they will continue to receive therapy until one of the above criteria applies.

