
Progressive disease (PD)¶¶, 
	
Any one or more of the following criteria:
 
 • Increase of 25% from lowest confirmed response value in one or more of the following criteria: 
 ○ Serum M-protein (absolute increase must be ≥ 0.5 g/dL) ○ Serum M-protein increase ≥ 1 g/dL, if the lowest M component was ≥ 5 g/dL; ○ Urine M-protein (absolute increase must be ≥ 200 mg/24 h); ○ In patients without measurable serum and urine M-protein levels, the difference between involved and uninvolved FLC levels. (absolute increase must be > 10 mg/dL); ○ In patients without measurable serum and urine M-protein levels and without measurable involved FLC levels, bone marrow plasma-cell percentage irrespective of baseline status (absolute increase must be $\geq 10\%$) ○ Appearance of a new lesion(s), $\geq 50\%$ increase from nadir in SPD§§ of >1 lesion, or $\geq 50\%$ increase in the longest diameter of a previous lesion >1 cm in short axis; ○ $\geq 50\%$ increase in circulating plasma cells (minimum of 200 cells per μL) if this is the only measure of disease=

Clinical Relapse
	
Clinical relapse requires one or more of the following criteria:
 
 • Direct indicators of increasing disease and/or end organ dysfunction (CRAB features) related to the underlying clonal plasma-cell proliferative disorder. It is not used in calculation of TTP or PFS but is listed as something that can be reported optionally or for use in clinical practice • Development of new soft tissue plasmacytomas or bone lesions (osteoporotic fractures do not constitute progression) • Definite increase in the size of existing plasmacytomas or bone lesions. A definite increase is defined as a 50% (and ≥ 1 cm) increase as measured serially by the SPD§§ of the measurable lesion • Hypercalcaemia (>11 mg/dL) • Decrease in hemoglobin of ≥ 2 g/dL not related to therapy or other non-myeloma-related conditions • Rise in serum creatinine by 2 mg/dL or more from the start of the therapy and attributable to myeloma; • Hyperviscosity related to serum paraprotein

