14.3.4 Progression Free Survival

Progression free survival (PFS) is defined as the duration of time from enrollment to the study (treatment start date) to first occurrence of either PD or death. Disease progression must be objectively determined per IMWG 2016 criteria (see Section 13.1), where the date of progression is the date of the last assessment that identified PD. If the subject died without documented disease progression, the date of progression will be the date of death. For surviving subjects who do not have documented disease progression, PFS will be censored at the date of last disease assessment. For subjects who receive subsequent anti-cancer therapy prior to documented disease progression, PFS will be censored at the date of last disease assessment prior to the commencement of subsequent therapy. Subjects who have an initial PFS event immediately following 2 or more consecutive missed disease assessments will be censored at the date of the last assessment prior to those missed assessments. For participants with only one missed assessment, the documented PD status and assessment date will be used.

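### The rules that end treatment and disease evaluation are wider than the PFS, TTP and DoR event, so some subjects can be censored at disease failure and these endpoints may be overstated

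*Combined protocol and SAP*

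**What the plan says.** Four parts of the combined protocol and SAP bear on this.

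- **Stopping treatment.** The first criterion in Section 9.1 is "Disease relapse or progression". It does not require confirmation.
- **Stopping disease evaluation.** Section 8.7 reads: "For subjects who discontinue study treatment before relapse or PD, disease evaluations should continue to be performed until relapse or confirmed PD". Death, new anticancer treatment, withdrawal of consent and the final-analysis criteria also end it. Footnote 6 of the Study Calendar (Section 7) follows the same pattern.
- **What counts as progression.** Section 14.3.4 takes PD from the IMWG 2016 criteria in Section 13.1. Calendar footnote 3 adds: "note that all response categories (CR, sCR, VGPR, PR, and PD) require 2 consecutive assessments". Section 13.1 treats every category except stable disease as unconfirmed until the repeat test is done. Of clinical relapse it says: "It is not used in calculation of TTP or PFS but is listed as something that can be reported optionally".
- **Censoring.** Section 14.3.4: "For subjects who receive subsequent anti-cancer therapy prior to documented disease progression, PFS will be censored at the date of last disease assessment", meaning the last assessment before that therapy began. Sections 14.3.5 and 14.3.6 carry the same censoring over to TTP and DoR.

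Relapse is not defined as an on-study term. The only general definition is the eligibility one in Section 3.2: "Relapse is defined as progression of disease after an initial response to previous treatment, more than 6 months after discontinuation of treatment".

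**The concern.** When the rule that ends observation is wider than the event being counted, some subjects leave observation because their disease has failed, yet no failure is recorded. Kaplan-Meier estimation assumes that a censored subject has the same outlook as those still at risk. A subject censored because the myeloma has returned does not, so the censoring is informative and pushes PFS, TTP and DoR upward.

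The study has a single arm, so no control group shares the bias, and readers are likely to set its PFS beside published KRd figures.

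**Working it through.** The plan gives no expected median, event count or power for PFS, TTP or DoR, so there is no stated figure to reproduce. The check has two parts.

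**1. Following the text for two kinds of subject**

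*Clinical relapse shown only by laboratory criteria.* Section 13.1 lists hypercalcaemia, a haemoglobin fall, a creatinine rise and hyperviscosity under clinical relapse, but not under PD.
- Section 9.1 allows treatment to stop at relapse.
- Section 8.7 requires further evaluation only for subjects who stopped before relapse or PD, and ends it at relapse.
- Section 13.1 keeps this event out of PFS and TTP.
- When new therapy starts, Section 14.3.4 censors the subject at the last earlier assessment.

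*First PD reading while on treatment.*
- Section 9.1 allows treatment to stop at progression, with no mention of confirmation.
- On a plain reading this subject did not stop before PD, so Section 8.7 does not require further evaluation.
- The calendar row for disease blood and urine is empty at the Safety Follow-up Visit and in Follow-up. Section 8.6 lists chemistries and a blood count, and Section 8.5 only a marrow at the investigator's discretion.
- No repeat M-protein or FLC test is therefore scheduled. If new therapy starts first, PD is never confirmed and the plan does not say how to classify the subject. Read with Section 13.1, the subject is censored.

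**2. Size**

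Inputs:
- True median PFS m: 15.4 months (phase II KRd cohort) or 26.3 months (phase III KRd arm), both from Section 1.2, used only as illustrations.
- Share q of failures censored at failure: **an assumption**, 5% to 30%. The documents give no value.

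With exponential times, hazard λ = ln 2 / m. If a random share q of failures is censored at the failure time, Kaplan-Meier estimates the hazard λ(1−q). The apparent median is then m/(1−q), and apparent 24-month PFS is 0.5^(24(1−q)/m).

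| q | m = 15.4: m/(1−q) | simulated | m = 26.3: m/(1−q) | simulated | Inflation 1/(1−q) − 1 |
|---|---|---|---|---|---|
| 5% | 15.4/0.95 = 16.2 | 16.0 | 26.3/0.95 = 27.7 | 27.0 | 5% |
| 10% | 15.4/0.90 = 17.1 | 17.2 | 26.3/0.90 = 29.2 | 28.9 | 11% |
| 20% | 15.4/0.80 = 19.25 | 19.3 | 26.3/0.80 = 32.9 | 33.1 | 25% |
| 30% | 15.4/0.70 = 22.0 | 21.9 | 26.3/0.70 = 37.6 | 37.9 | 43% |

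The simulated columns are the median Kaplan-Meier median over 2,000 trials of 40 subjects, with follow-up uniform from 36 to 60 months (24 months of accrual plus 3 years). With q = 0 they gave 14.8 and 25.4.

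At q = 20%, 24-month PFS reads 0.42 instead of 0.34 (m = 15.4), or 0.60 instead of 0.53 (m = 26.3).

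**Timing of the updated analysis.** Section 14.5.1 triggers it at 20% PFS censoring (8 of 40) or at 3 years on study, whichever comes sooner. In the same simulation, mean censoring with q = 0 was 12% (m = 15.4) and 29% (m = 26.3). With m = 15.4 it rose to 17% at q = 5% and 21% at q = 10%.

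**The case against.** The case against has real force on several points.

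- **Relapse may simply mean PD.** Section 3.2 defines relapse as a form of progression, and new or growing lesions appear under both headings in Section 13.1. Measurable disease is required and non-secretory myeloma is excluded, so a relapse with no paraprotein or FLC progression may be uncommon. This narrows the first route without closing it: Section 8.7 sets relapse beside confirmed PD as if they differed, and the laboratory-only criteria remain.
- **A first PD reading might not count as PD.** Because Section 13.1 calls it unconfirmed, such a subject could be said to have stopped before PD and so to stay under evaluation. Section 13.1 sets no minimum interval for the repeat, and Section 8.7 allows chart review, which could capture a repeat done in routine care. The reading is possible, but Section 8.7 uses unqualified PD to say who enters follow-up and confirmed PD to say when it ends. The second route is thus an inference from missing scheduling, not an explicit instruction.
- **Death can restore an event.** Death without documented PD counts for PFS and DoR, subject to the rule on two or more missed assessments. It does not help once censoring at new therapy has applied.
- **Consequence.** These endpoints are only estimated. The one formal test is on VGPR+.

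A reader might infer that follow-up evaluation ends at a first PD reading. Section 8.7 says confirmed PD, so it does not. A reader might also infer that the 20% trigger becomes unreachable and the updated analysis is lost. The 3-year alternative bounds any delay, and with a 26.3-month median that limit would be expected to govern even with q = 0.

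**Conclusion.** The mismatch is real. Following the text as written can censor a subject at disease failure by either route, and the resulting bias in PFS, TTP and DoR is upward for any q above zero. The supportable conclusion is that these endpoints **may be** overstated. The documents do not show that they are, because q is unknown and could be small.

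For assumed q of 5% to 30%, the median rises by 5% to 43%: to 16.2–22.0 months from 15.4, or 27.7–37.6 months from 26.3. This rests on exponential times, loss unrelated to time on study, and censoring at the failure itself; in practice the censoring date is the last disease assessment. Whether the study would look better than published KRd results for this reason alone also depends on how those trials counted events, which the documents do not show.

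VGPR+, ORR and OS are unaffected, and TTNT still records the new therapy. This is a cheap improvement to secondary endpoints, not a threat to the primary result.

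**What to change.** 1. In Section 8.7 and calendar footnote 6, drop relapse as an end point for disease evaluation. Continue to confirmed IMWG PD for every subject who stops treatment without it, leaving the other listed end points in place. Add a repeat M-protein/FLC test to the blood draw at the Safety Follow-up Visit, or take it earlier if new therapy is about to start.
2. Keep the IMWG-confirmed definition in Sections 14.3.4 to 14.3.6 for the main analysis. Add a sensitivity analysis of PFS, TTP and DoR that counts as events (a) clinical relapse leading to treatment stop or new therapy, and (b) a single PD reading followed by new therapy or by no further assessment. Making (b) the main analysis would depart from the two-assessment rule in Section 13.1, so it belongs in the sensitivity analysis.
3. The sponsor must reconcile the stopping wording in Section 9.1 with Section 13.1 and say what relapse means on study. Which treatment rule applies is for the sponsor to decide.

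Cost: wording in a few sections, one extra tube at an existing draw (or a slightly earlier one), a little more analysis, and possibly a shorter reported PFS.

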9.2 Off Study

Subjects will remain on study until the criteria for the final analysis have been met.

Reasons a subject may be removed from the study early include, but are not limited to:

- Subject non-compliance with study participation, in the opinion of the investigator
- The subject or legal representative (such as a parent or legal guardian) withdraws study consent
- The subject is lost to follow-up
- Investigator's decision to withdraw the subject
- Subject death
- Early study termination

When subjects are removed from the study, the reason for study removal and date the subject was removed should be documented.

Subjects that are Off Study will not participate in any study related procedures, including data collection.

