14.3.3 Overall Survival

Overall survival (OS) is defined as the duration from enrollment to the study (treatment start date) to the date of death from any cause. Subjects who are alive or lost to follow-up at the time of the analysis will be censored at the last known date they were alive.

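### One failed contact round can end survival follow-up, and no vital-status check is required before a subject is declared lost or before overall survival is analysed

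*Combined protocol and SAP*

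**What the plan says.** Section 8.7 (Follow-up) sets the contact schedule and its end points: "Survival follow-up will occur every 3 months (+/- 30 days) from the last administration of protocol-directed therapy until death, lost to follow-up", or until the final-analysis criteria are met. If a subject cannot be reached after "three attempted telephone calls over a period of 10 business days, the subject will be contacted in writing". The section then gives the definition: "Lost to follow-up is defined as four consecutive unsuccessful documented attempts (telephone and written) to contact the subject".

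The same section points the other way in two places. It keeps the site responsible: "The investigator is responsible for following the subject during the required follow-up period even if the subject lives elsewhere". It also permits other sources: "Follow-up clinical information may also be obtained through chart reviews or other data sources (e.g. death registries").

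Section 9.2 (Off Study) lists loss to follow-up among the reasons for which a subject may be removed early, and adds: "Subjects that are Off Study will not participate in any study related procedures, including data collection".

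Footnote 6 of the Study Calendar (Section 7) gives the same 3-month schedule but a different end: "from the last administration of protocol-directed therapy or until death, and may be conducted via telephone". Loss is not mentioned there.

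Section 14.3.3 says that subjects "lost to follow-up at the time of the analysis will be censored at the last known date they were alive". Section 14.3.7 censors time to next treatment (TTNT) at last contact for survivors with no subsequent therapy. Section 14.5.1 triggers the final analysis at a 20% OS censoring rate or at 5 years on study. Lost and withdrawn subjects do not count towards the 5-year condition.

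**The concern.** OS is meant to be followed for up to 5 years, largely by quarterly telephone contact. A site that applies 8.7 as written can stop that follow-up after one unsuccessful round. If it then takes the subject Off Study under 9.2, it may not collect data from the registry or chart that 8.7 allows. Another site, reading footnote 6, would carry on. The same subject could be handled in two ways, and nothing in the analysis section settles which.

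In relapsed myeloma, a subject may be unreachable because of hospital care, hospice care or death. Loss that is unrelated to prognosis costs only precision. Loss that is caused by death or decline is informative: a death that should be an event becomes a censored observation, and the Kaplan-Meier curve sits too high. TTNT is exposed in the same way, because a next treatment started after contact fails may go unrecorded.

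**Working it through.** The documents give no expected loss rate and no figure for missed deaths, so there is no planned number to reproduce. The check has three parts.

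**1. The passages side by side.**

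| Question | 8.7 | 9.2 | Calendar footnote 6 |
|---|---|---|---|
| Does loss end survival follow-up? | Yes, listed as an end point | Loss is a permitted reason for removal | Not listed |
| May data still be collected after loss? | Charts and registries permitted | Not once Off Study | Silent |
| Is a retry at the next 3-month contact required? | Not stated | Not stated | Not stated |
| Is a vital-status check required before loss is declared? | No, optional | No | No |

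Sections 14.3.3 and 14.5.1 require no vital-status check before an OS analysis either.

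**2. Timing.** The telephone phase is 10 business days, about 12 to 14 calendar days. The contact window is 30 days either side, a span of 60 days. The calls can therefore all fall inside one open window. The letter has no response period, so the total time to a declaration of loss cannot be computed.

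**3. Possible size of the OS bias (illustration only).**

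Input from the documents: 24-month OS of 73.3% in the KRd arm of the phase III trial (Section 1.2). Assumptions: exponential survival; a share q of deaths is missed; those subjects are censored shortly before death; nothing is recovered from charts or registries.

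- Monthly hazard: −ln(0.733)/24 = 0.01294.
- True 5-year OS: exp(−0.01294 × 60) = 0.460.
- If a share q of deaths after month 24 is missed, the observed hazard after month 24 is (1 − q) times the true one, so the estimate is 0.733 × exp(−0.01294 × 36 × (1 − q)).
  - q = 10%: 0.482, which is 2.2 points too high.
  - q = 20%: 0.505, which is 4.5 points too high.
- If the share applies to all deaths from the start, the estimate is 0.460 raised to the power (1 − q): 47.8%, 49.7% and 53.7% for q = 5%, 10% and 20%, or 1.8, 3.7 and 7.7 points too high. This is the less realistic case, because subjects on treatment are seen every cycle.

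For scale, the binomial standard error at 46% with 40 subjects is √(0.46 × 0.54/40) = 0.079, or 7.9 points.

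**Timing of the final analysis.** Taking 40 subjects, 20% censoring means 0.80 × 40 = 32 deaths. More than 8 subjects censored without later recovery would put that trigger out of reach. On the illustrative curve only about 40 × (1 − 0.460) = 21.6 deaths are expected by 5 years, so the 5-year rule would probably govern in any case, and that rule passes over lost subjects.

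**The case against.** Much can be said for the plan. Section 8.7 names chart reviews and death registries, and keeps the investigator responsible when a subject moves or is treated elsewhere. Removal under 9.2 is permitted, not automatic. Section 14.3.3 refers to loss as it stands at the analysis, and it credits no survival time beyond the last date known alive. OS is a secondary Kaplan-Meier estimate with no hypothesis test or comparator arm, and the illustrated bias is smaller than one standard error in the main case.

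These points stand, and they rule out several stronger readings that a reader might infer:

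- *The whole process is shorter than the contact window.* This is shown only for the calls. The letter has no response time, and the text does not say when in the window the calls begin.
- *Loss ends follow-up permanently.* The documents do not say so. Removal is permissive, footnote 6 does not stop at loss, and nothing forbids taking a subject back. What is missing is any instruction to try again.
- *Every death not notified to the site is censored.* Charts and registries may be searched. Bias needs loss related to death and no such search.
- *A definite number of living subjects will be lost.* A count such as 3 to 11 of 40 comes from assuming 1% to 2% unreachable at each of 8 to 16 off-treatment contacts for everyone. The documents give no such rate. Treatment also continues to progression and some subjects die, so many would have fewer contacts.

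What the objection does not remove is that the search is optional, is tied neither to declaring loss nor to an analysis, and is barred once 9.2 is applied.

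**Conclusion.** The point holds in limited form. The text allows one failed contact round to end survival follow-up, 8.7 conflicts with 9.2 and with calendar footnote 6, and no vital-status check is required at any stage. OS can therefore be overstated through informative censoring.

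The size is unknown. About 2 to 4.5 points at 5 years follows only if survival is exponential through the quoted 24-month figure, 10% to 20% of deaths after month 24 are missed, and none is recovered. With full recovery from charts or registries the bias would be zero.

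The effect is confined to secondary long-term endpoints: mainly OS, then TTNT and the timing of the final analysis. The VGPR+ endpoint is read after four induction cycles and is untouched. This is a cheap improvement worth making, not a threat to the trial's main conclusion.

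**What to change.** 1. Reconcile 8.7, 9.2 and calendar footnote 6 so that they agree on whether loss ends survival follow-up, and state how long to wait for a reply to the letter.
2. In 8.7, keep attempting the later scheduled 3-month contacts after a failed round, and return the subject to follow-up if reached.
3. Require a chart and death-registry check, as consent allows, before loss is treated as final and before each OS analysis.
4. Remove loss to follow-up from the 9.2 reasons that stop data collection.

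The cost is protocol wording and slightly more coordinator time for calls and record checks, using sources that 8.7 already permits. Sample size and the primary analysis do not change.
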